6.1.3 Definition of Baseline

Baseline is defined as the last measurement collected on or prior to randomization date for SMT Alone, and as the last measurement obtained before the initiation of treatment (date/time) for SMT+PE-A 5%. "For SMT+PE-A 5% subjects, two sets of vital signs assessments are collected on Day 1; the time of vital signs assessment, as well as the time for lab assessment, including chemistry, coagulation and hematology parameters will be used to determine whether the vital signs or lab were collected pre- or post- Albutein administration, if assessment time is not available, then the vital signs or lab designated by the investigator as pre-dose on the Electronic Case Report Form (eCRF) will be considered baseline.

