6.1.5 Visit Windows

As subjects do not always adhere to visits as scheduled in the study protocol, the following rules will be applied to map each subject's assessment visits to analysis visits, based on the timing of their assessment visits, relative to their Study Day 1. Visit mapping is applied to all visits (scheduled, unscheduled, hospital discharge and early termination) for laboratory assessments, vital sign assessments and exploratory endpoint assessments. Due to differences in visit schedules for the

assessments, distinct mapping methods are used for each type of assessment. A detailed list of the parameters and the mapping rules to be applied is provided in [Appendix 5](#). In cases where multiple assessments for a parameter are recorded within a single visit window, distinct rules are applied to laboratory assessments, vital signs, and exploratory endpoints, respectively because lab parameters and vital signs are measured before and after exchanges for SMT+PE 5% group.

For laboratory and vital sign assessments:

- In the treatment period, if 2 or more assessments are mapped to the same visit window where an exchange occurred. Take the assessment closest to the scheduled exchange date/time visit target day to be used in the analysis.
- If 2 or more assessments are mapped to the same visit window, then the non-missing assessment closest to the scheduled visit target day will be used in the analysis.
- If 2 assessments are equidistant from the visit target day, the later non-missing observation will be used in the analysis.
- If in the treatment period, two assessments occur on the same date and the above rules cannot be applied to identify a record to be used in the analysis, take the treatment scheduled timepoint visit in the analysis.
- For safety laboratory visits, if the screening and Treatment Day 1 visit occur on the same date and time use the ascension number to determine if this is a duplicate visit and only pick one record.

For exploratory endpoints:

- If 2 or more assessments are mapped to the same visit window, then the non-missing assessment closest to the scheduled visit target day will be used in the analysis.
- If 2 assessments are equidistant from the visit target day, the later non-missing observation will be used in the analysis.

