9.3.2 CLIF-C OF Score and Sub Scores for Organ Function

CLIF-C OF scores evaluated at baseline (last measurement taken prior to treatment day 1), during and after the treatment period, and at the end of hospitalization (or before liver transplantation or death) will be listed.

The CLIF-C OF score system consists of six sub-scores for liver, kidney, brain, coagulation, circulatory, and respiratory organs/systems - each with values of 1, 2 or 3 with a higher number representing more severe disease.

Each CLIF-C OF sub-score will be summarized as a categorical variable by treatment for each visit. The CLIF-C OF sub-scores will be compared at visits when the data are collected for both treatment groups using the generalized linear models implemented in SAS GENMOD procedure, in which the CLIF-C OF sub-score is modeled by the proportional odds cumulative logit model for ordinal data with adjustment for baseline sub-score, region (Europe of North America) and ACLF subgroup (ACLF-1B, ACLF-2, or ACLF-3a) treatment, visit and treatment-by-visit interaction, as independent variables), and the robust variance estimate for the treatment effect will be estimated based on the independent working correlation structure.

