The total CLIF-C OF score is a discrete numeric value in the range of 6 to 18 (inclusive) and is defined as the sum of the six organ/system sub-scores. If an individual sub-score is missing, the total score will also be missing. The total CLIF-C OF score and change in total score from baseline to each scheduled post-baseline visit will be summarized, as a continuous variable, by treatment and scheduled visit, excluding visits that follow liver transplantation. In addition, the total score change from baseline for scheduled visits with data for both treatment groups will be analyzed by MMRM, which includes change from baseline as the dependent variable; treatment, visit, region (Europe of North America) and ACLF subgroup (ACLF-1B, ACLF-2, or ACLF-3a), treatment-by-visit interaction, region-by-visit interaction, and ACLF subgroup (ACLF-1B, ACLF-2, or ACLF-3a)-by-visit interaction as fixed effects; baseline and baseline-by-visit as covariates; and measures within-subject at each visit as a repeated measure. The model employs an unstructured covariance matrix for the within-subject dependence. The treatment effect will be evaluated using the full model, with no backward or stepwise selection methods. If the model fails to converge, the mixed effects model with a compound symmetry correlation structure will be used.

Assessments after Liver transplant will be removed from summaries and analysis.

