9.3.3 CLIF-C ACLF Score

The CLIF-C Acute-on-Chronic Liver Failure (ACLF) score is a continuous numeric value in the range of 0-100 with a higher number representing more severe disease, derived from the CLIF-C OF total score, and is defined as:

$$\text{CLIF-C ACLF} = 10 * [0.33 * \text{CLIF-C OFs} + 0.04 * \text{Age \{years collected on the demographics eCRF page\}} + 0.63 * \text{Ln}(\text{white cell count \{10}^9 \text{ cells/L\}}) - 2]$$

The CLIF-C ACLF score will be included in the listing of CLIF-C OF scores and will be summarized as a continuous variable. The total score and change in total score from baseline (last measurement taken prior to the start of study treatment for SMT+PE 5% group and last measurement on or prior to the randomization date for SMT alone) to each post-baseline scheduled visit will be summarized by treatment and each visit. In addition, the MMRM analysis of CLIF-C OF scores will be repeated for change from baseline CLIF ACLF total score.

Assessments after Liver transplant will be removed from summaries and analysis.

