9.3.4 MELD Score

The Model for End-stage Liver Disease (MELD) score is a continuous numeric value in the range of 6-40, with a higher number representing more severe disease, and is defined as:

$$\text{MELD} = 9.57 \cdot \ln(\text{Creatinine \{mg/dl\}}) + 3.78 \cdot \ln(\text{Bilirubin \{mg/dl\}}) + 11.2 \cdot \ln(\text{INR}) + 6.43$$

If any of the individual clinical parameters used to derive the MELD score report results <1, the result is imputed to 1. For creatine reported >4, the result is imputed to 4(8). These parameters are then used to derive the MELD score. Any final MELD score >40 will be rounded to 40. MELD scores are evaluated monthly through Month 12 and will be listed.

The MELD score will be summarized as a continuous variable. The MELD total score and change in total score from baseline ((last measurement taken prior to the start of study treatment for SMT+PE 5% group and last measurement prior to randomization date for SMT alone) to each scheduled post-baseline visit will be summarized, as a continuous variable, by treatment and scheduled visit. In addition, the MMRM analysis of CLIF-C OF scores will be repeated for the change from baseline total scores.

Assessments after Liver transplant will be removed from summaries and analysis.

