9.3.6 Systemic Inflammation Assessment

CRP [in chemistry panel], WBC [in hematology panel] and procalcitonin are analyzed by a central laboratory and collected on treatment Day1, Day2, then on every other treatment day and each follow-up visit.

A summary table will present descriptive statistics by visit for original values and change from baseline. For the SMT+PE-A 5% group, change in value from baseline to the pre-exchange timepoint will be summarized.

Moreover, the difference between pre-exchange and post-exchange within each visit will also be summarized.

The MMRM analysis of CLIF-C OF scores will be repeated here to analyze the change from baseline value for inflammatory biomarkers. for the SMT PE-A 5% group, the change from baseline to pre-exchange timepoint will be used for this analysis.

Assessments after Liver transplant will be removed from summaries and analysis.

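### SAP 9.3.4 gives MELD a baseline that differs by arm; the score sections also leave exchange-day timing open and give the MMRM only a compound-symmetry fallback without robust standard errors

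*SAP*

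**What the plan says.** **Baseline.** SAP 6.1.3 gives the general rule for the control arm: "Baseline is defined as the last measurement collected on or prior to randomization date for SMT Alone". For the plasma-exchange arm it takes the last value before treatment starts. The score sections then restate baseline in different ways:

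- MELD (SAP 9.3.4): "last measurement taken prior to the start of study treatment for SMT+PE 5% group", but "last measurement prior to randomization date for SMT alone".
- CLIF-C ACLF (SAP 9.3.3): same rule for the exchange arm, but "last measurement on or prior to the randomization date for SMT alone".
- CLIF-C OF (SAP 9.3.2): "CLIF-C OF scores evaluated at baseline (last measurement taken prior to treatment day 1", with no distinction by arm. Child-Pugh (SAP 9.3.5) uses the same cut-off.
- SAP Appendix 5, exploratory endpoints: one baseline window, Day 1 or earlier, for everyone.
- Protocol 9.1.2.4: one rule for both arms, the last value before study treatment starts on Day 1.

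**Exchange days.** For inflammation markers, SAP 9.3.6 says that in the exchange arm "the change from baseline to pre-exchange timepoint will be used for this analysis". SAP 9.3.12, 10.3 and 10.4 also use pre-exchange values for change from baseline in albumin, laboratory tests and vital signs. SAP 9.3.2 to 9.3.5 say nothing on this. The record-selection rules for exploratory endpoints in SAP 6.1.5 do not separate pre- from post-exchange values. They add: "If 2 assessments are equidistant from the visit target day, the later non-missing observation will be used in the analysis".

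**Model.** SAP 9.3.2 specifies an MMRM with unstructured covariance for the CLIF-C OF total. Sections 9.3.3 to 9.3.6 reuse it. The only alternative is: "If the model fails to converge, the mixed effects model with a compound symmetry correlation structure will be used". Robust variance is specified for the ordinal sub-score model, not for the MMRM.

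**The concern.** The protocol describes ACLF as very dynamic, and screening may run up to 10 days before Day 1. If one arm's MELD baseline must predate randomization day and the other's may be taken on that day, the two change scores cover different intervals, and any drift before randomization enters the treatment comparison.

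MELD, Child-Pugh and the CLIF-C scores are built partly from bilirubin, INR or albumin, which a plasma exchange alters directly. A score computed from post-exchange components would partly measure the procedure rather than recovery.

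Compound symmetry assumes one variance from Day 2 to Day 90. If that is wrong and the standard errors are model-based, follow-up visits may look more significant than they are.

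**Working it through.** The documents state no sample size, power or error rate for the score analyses, so there is no plan figure to reproduce.

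**1. Baseline.** Can a randomization-day value be the baseline?

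- SAP 6.1.3 and 9.3.3: yes in both arms (before first exchange in the exchange arm).
- SAP 9.3.4, MELD: no for SMT, yes for the exchange arm.
- SAP 9.3.2 and 9.3.5: no in either arm, so these are symmetric but conflict with 6.1.3.
- SAP Appendix 5 and protocol 9.1.2.4: yes in both arms.

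Only MELD is asymmetric. Let δ be the mean rise in MELD from the earlier value to Day 1, and β the slope of the later score Y on the Day 1 baseline B. Treating the shift as constant, the SMT analysis uses B* = B − δ.

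- Unadjusted: SMT change is Y − B* = (Y − B) + δ, so the difference (exchange minus SMT) shifts by −δ.
- With baseline as covariate: SMT follows Y = a + βB = a + βδ + βB*, so the difference shifts by −βδ.

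Adjustment scales the bias by β; it does not remove it unless β or δ is 0. The documents give neither quantity, so size and direction are unknown. Appendix 5 also allows screening and Day 1 to share a date. Under the literal 9.3.4 rule, an SMT subject with no earlier score would then have no MELD baseline.

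**2. Exchange-day components.** Inputs: 1.2 plasma volumes per session (protocol 6.1.1.1) and the bilirubin term 3.78 × ln(bilirubin) in MELD (SAP 9.3.4). If a fraction f is retained, MELD shifts by 3.78 × ln(f), provided the floor of 1 and the cap of 40 do not apply.

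- f = 0.80: −0.8
- f = 0.60: −1.9
- f = 0.50: −2.6
- f = exp(−1.2) = 0.301, ideal one-compartment exchange without rebound: −4.5

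The retained fractions are assumptions. For Child-Pugh, the pilot's albumin rise from 24 to 28 g/L (protocol 2.2) crosses the 2.8 g/dL cut in SAP Appendix 4 and moves the sub-score from 3 to 2. The protocol does not present that rise as a within-session change, so it is only illustrative.

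**3. Fallback covariance.** Scores are recorded on Days 2 to 17 (16 visits) and Days 21, 28, 60 and 90 (4), so 20 post-baseline visits.

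- Unstructured: 20 × 21/2 = 210 covariance parameters; compound symmetry: 2.
- Fixed effects per visit: intercept 1, treatment 1, region 1, ACLF grade 2, baseline 1 = 6; 6 × 20 = 120.

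Non-convergence is therefore plausible, though not established. With r the ratio of model-based to true standard error, type I error is 2 × (1 − Φ(1.96 r)). Without dropout, compound symmetry pools the visit variances. If the SD rises linearly from 1 to 1.5, the mean variance is about 1.59 and its root 1.26, so r = 1.26/1.5 = 0.84 at the last visit and type I error is 0.10.

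Results at the last visit under assumed covariances (AR(1) adjacent-visit correlation 0.80 to 0.95; dropout random and monotone):

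- Compound symmetry true, 0% or 40% dropout: r = 1.00; 0.05.
- AR(1), equal variances, no dropout: r = 1.00; 0.05.
- AR(1), equal variances, 40% dropout: r = 0.88 to 0.91; 0.074 to 0.084.
- SD rises 1.5-fold, no dropout: r = 0.84; 0.10. With 40% dropout: r = 0.75 to 0.77; 0.13 to 0.14.
- SD doubles, no dropout: r = 0.77; 0.134. With 40% dropout: r = 0.68 to 0.70; 0.17 to 0.18.

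Where the SD rises, the first visit errs the other way (r = 1.24 to 1.53). The plan's own mortality assumptions of 50% and 35% average 42.5% by Day 90, so 40% loss is a realistic amount, but death is not random dropout.

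**The case against.** The MELD wording is probably a slip. SAP 6.1.3, 9.3.3 and Appendix 5 all admit Day 1, and eligible subjects are included at diagnosis, so many gaps may be short. That is fair, but the SAP does not say which rule prevails, and 9.3.4 is the section a programmer would follow for MELD.

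A reader might infer that every severity score has an arm-specific baseline. The text does not support that: CLIF-C OF and Child-Pugh apply one rule to both arms, and CLIF-C ACLF admits a Day 1 value in both.

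A reader might also infer that post-exchange scores will be analysed. The SAP does not plan this. Its visit schedule (5.2.2) lists severity scoring apart from the items measured before and after each exchange, and the scores use local results (protocol Table 7-1, footnote a), so the paired draws need not feed them. The tie rule matters only if two scores fall in one window, and treatment-day windows are one day wide. What stands is that score timing relative to the exchange is unspecified.

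Finally, the fallback applies only on non-convergence, and its standard errors are correct if compound symmetry holds. The sub-score comparisons already have robust variance. These points stand and limit the claim to a conditional risk in the MMRM analyses.

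**Conclusion.** The firm defect is the MELD baseline: as written it differs by arm and contradicts the rest of the SAP and the protocol. The bias is δ without adjustment and roughly βδ with it, neither of which the documents let us quantify. The Child-Pugh and CLIF-C OF baseline wording is a lesser fault, a conflict with SAP 6.1.3 without an arm difference.

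The exchange-day gap is an omission. It would matter by about 0.8 to 4.5 MELD points from bilirubin, but only if post-exchange components were used and 80% to 30% of bilirubin were retained. The covariance fallback could leave last-visit type I error anywhere from the nominal 5% to about 18%, depending on a covariance the documents do not describe.

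It would go too far to call the MELD, Child-Pugh and CLIF-C results unreliable. All are exploratory and outside the fixed-sequence procedure, and the survival tests are untouched.

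**What to change.** - **Baseline.** State one rule in SAP 6.1.3 and cite it from 9.3.2 to 9.3.5: last value on or before randomization and, in the exchange arm, before the first exchange. Delete the section-specific versions and align Appendix 5. For the exchange arm this tightens 6.1.3, which now admits a value after randomization if the first exchange is later. Correct the statement in 9.3.4 that MELD is evaluated monthly through Month 12, which does not fit a 90-day study.
- **Exchange days.** State that exchange-arm scores on those days use pre-exchange component values. Where the timing of a local result cannot be established, flag it and add a sensitivity analysis without those records.
- **Model.** Before compound symmetry, insert heterogeneous structures, for example heterogeneous Toeplitz, then heterogeneous AR(1) or spatial power. Use sandwich standard errors for any fit that is not unstructured.
- **Keep** the between-arm comparisons during the treatment period. Protocol 9.1.2.4 specifies them, and reducing them to description would depart from it.

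The cost is minor SAP wording and programming. The trial is open-label and its last patient visit has taken place, so the change should be dated and made before these analyses are run.

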9.3.5 Child-Pugh Score

The Child-Turcotte-Pugh (Child-Pugh) classification for severity of cirrhosis consists of 5 sub-scores for encephalopathy, ascites, bilirubin, albumin, and INR – each with values of 1, 2 or 3 with a higher number representing more severe disease. Refer to [Appendix 4](#) for details. The Child-Pugh Score is a discrete numeric value in the range of 5 to 15 (inclusive) and is defined as the sum of the five sub-scores. If an individual sub-score is missing, the total score will also be missing.

The Child-Pugh Class is derived from the Child-Pugh Score as follows: Class A = score of 5-6; Class B = score of 7-9; Class C = score of 10-15.

Child-Pugh scores are evaluated for each visit and will be listed.

Each Child-Pugh sub-score will be summarized as a categorical variable by treatment and scheduled visit. In addition, each Child-Pugh sub-score will be compared by treatment and scheduled visit using the same methods as for CLIF-C OF sub-scores (see section [9.3.2](#)).

The Child-Pugh Total score and change in total Score from baseline (last measurement taken prior to treatment day 1) to each scheduled post-baseline visit will be summarized as a continuous variable, by treatment group and scheduled visit. In addition, the MMRM analysis of CLIF-C OF scores will be repeated for the change from baseline total scores.

The Child-Pugh Class will be summarized as a categorical variable by treatment for each visit.

Assessments after Liver transplant will be removed from summaries and analysis.

9.3.6 Systemic Inflammation Assessment

CRP [in chemistry panel], WBC [in hematology panel] and procalcitonin are analyzed by a central laboratory and collected on treatment Day1, Day2, then on every other treatment day and each follow-up visit.

A summary table will present descriptive statistics by visit for original values and change from baseline. For the SMT+PE-A 5% group, change in value from baseline to the pre-exchange timepoint will be summarized.

Moreover, the difference between pre-exchange and post-exchange within each visit will also be summarized.

The MMRM analysis of CLIF-C OF scores will be repeated here to analyze the change from baseline value for inflammatory biomarkers. for the SMT PE-A 5% group, the change from baseline to pre-exchange timepoint will be used for this analysis.

Assessments after Liver transplant will be removed from summaries and analysis.

9.3.7 ACLF Course at the End of Hospitalization

ACLF course includes resolution, improvement, steady course, or worsening from the baseline assessment. Resolution means ACLF grade changes to “No ACLF”. Improvement means ACLF grade becomes lower, steady course means ACLF grade does not change, while worsening means ACLF grade gets higher (see Table 9-1 for ACLF grades). ACLF Course will be summarized by visit, and at the end of hospitalization i.e. hospital discharge visit. The ACLF course at the hospital discharge visit will be compared between treatment groups using the Chi-square test or Fisher’s Exact test. In addition, shifts from baseline ACLF grade with categories (No ACLF, ACLF-1b, ACLF-2 and ACLF-3a) will be presented by analysis visit and treatment and the hospital discharge visit.

Assessments after Liver transplant will be removed from summaries and analysis.

Table 9-1 Grades of ACLF

Grades of ACLF	
No ACLF	
 - No organ failure - One organ failure (liver failure, coagulation, circulatory or respiratory failure) with creatinine <1.5 mg/dL and no HE
ACLF grade 1a	- Single kidney failure without mild or moderate HE
ACLF grade 1b	- Single organ failure with serum creatinine ranging from 1.5 mg/dL to 1.9 mg/dL and/or mild-to-moderate HE
ACLF grade 2	- Presence of 2 organ failures
ACLF grade 3a	- Presence of 3 organ failures
ACLF grade 3b	- Presence of ≥4 organ failures

9.3.8 Organ Failure at the End of Hospitalization

Organ failure is defined according to the CANONIC study criteria for each of the following organs/systems: liver, kidney, brain, coagulation, circulatory, and respiratory. Kidney failure is defined as CLIF-C OF sub-score of 2 or 3; for all others, organ failure is defined as CLIF-C OF sub-score of 3. Refer to [Appendix 4](#) for additional details. The number and percentage of subjects experiencing organ failure will be summarized for each organ by visit, and at the end of hospitalization i.e. hospital discharge visit. The percentage of subjects with each organ failure at end of hospitalization will be compared between treatment groups using the Fisher’s Exact or Chi-square test.

Assessments after Liver transplant will be removed from summaries and analysis.

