7.1.3 Exploratory Efficacy Variables

- Time to death through Day 90, time to transplant or death through Day 90, and time to death through Day 28 after randomization in subgroups of subjects with ACLF-1b, ACLF-2, or ACLF-3a.
- Time to death and time to transplant or death through in-patient hospital stay (including ICU stay) in the entire study population and in the subgroups of subjects with ACLF-1b, ACLF-2, or ACLF-3a.
- Time to transplant or death through Day 28 after randomization in the entire study population and in the subgroups of subjects with ACLF-1b, ACLF-2, or ACLF-3a.
- Incidence of individual organ failures: liver, renal, brain, coagulation, circulation and respiration, as defined by the CLIF-C OF score and the total CLIF-C OF score, during the treatment period and at the end of treatment, and of hospitalization (or liver transplantation or death).
- ACLF course (resolution, improvement, steady course, or worsening), score, CLIF-C ACLF score, Child-Pugh score, and MELD score
- Systemic inflammation as measured by CRP, WBC, and procalcitonin
- Rate of all new infections.
- Time-to-hospital discharge.
- Albumin levels in serum measured pre and post PE-A 5% to monitor the status of infused albumin in subjects during the course of the study.

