4.1.3 Exploratory Efficacy Objectives

The effects of SMT+PE-A 5% on the following parameters will be evaluated:

- 90-day overall, 90-day transplant-free, and 28-day overall survival after randomization in subgroups of subjects with ACLF-1b, ACLF-2, or ACLF-3a
- In-patient hospital stays (including ICU stay) overall and transplant-free survival in the entire study population and in the subgroups of subjects with ACLF-1b, ACLF-2, or ACLF-3a
- 28-day transplant-free survival in the entire study population and in the subgroups of subjects with ACLF-1b, ACLF-2, or ACLF-3a
- Incidence of individual organ failures: liver, renal, brain, coagulation, circulation, and respiration as defined by the Chronic Liver Failure-Consortium Organ Failure (CLIF-C OF) score and the total CLIF-C OF score, during the treatment period and at the end of treatment and of hospitalization (or liver transplantation or death)
- ACLF course (resolution, improvement, steady course, or worsening), CLIF-C ACLF score, Child-Pugh score, and Model for End-stage Liver Disease (MELD) score
- Systemic inflammation as measured by C-reactive protein (CRP), white blood cells (WBC), and procalcitonin
- Rate of all new infections
- Time to hospital discharge
- Pre and post PE-A 5% albumin levels in serum

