5.4 Study Variables

5.4.1 Efficacy Variables

The following efficacy variables will be assessed in this study:

- **Primary Efficacy**
 - Time to death through Day 90 after randomization of SMT+PE-A 5% versus SMT alone
- **Secondary Efficacy**
 - Time to liver transplant or death through Day 90 after randomization of SMT+PE-A 5% versus SMT alone
 - Time to death through Day 28 after randomization of SMT+PE-A 5% versus SMT alone
- **Exploratory Efficacy**
 - Time to death through Day 90, time to transplant or death through Day 90, and time to death through Day 28 after randomization in subgroups of subjects with ACLF-1b, ACLF-2, or ACLF-3a
 - Time to death and time to transplant or death through in-patient hospital stay (including ICU stay) in the entire study population and in the subgroups of subjects with ACLF-1b, ACLF-2, or ACLF-3a
 - Time to transplant or death through Day 28 after randomization in the entire study population and in the subgroups of subjects with ACLF-1b, ACLF-2, or ACLF-3a
 - Incidence of individual organ failures: liver, renal, brain, coagulation, circulation, and respiration, as defined by the CLIF-C OF score and the total CLIF-C OF score, during the treatment period and at the end of treatment, and of hospitalization (or liver transplantation or death)
 - ACLF course (resolution, improvement, steady course, or worsening), CLIF-C ACLF score, Child-Pugh score, and MELD score
 - Systemic inflammation as measured by CRP, WBC, and procalcitonin
 - Rate of all new infections
 - Time-to-hospital discharge
 - Albumin levels in serum measured pre and post PE-A 5% to monitor the status of infused albumin in subjects during the course of the study

Instituto Grifols, S.A. / Protocol IG1407

- Ascites Assessment

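### SAP 9.3.8 tests organ failure only at the discharge visit, although its endpoint extends to transplantation or death; with the same limit on ACLF course in 9.3.7, both tests depend on survival to discharge

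*SAP*

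**What the plan says.** **Organ failure, endpoint.** SAP 4.1.3 places the incidence of individual organ failures "during the treatment period and at the end of treatment and of hospitalization (or liver transplantation or death", closing the bracket there. SAP 5.4.1 and Protocol 7.1.3 say the same.

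**Organ failure, analysis.** SAP 9.3.8 has the counts "summarized for each organ by visit, and at the end of hospitalization i.e. hospital discharge visit" and adds: "The percentage of subjects with each organ failure at end of hospitalization will be compared between treatment groups", by Fisher's exact or Chi-square test.

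**ACLF course, endpoint.** The line reads "ACLF course (resolution, improvement, steady course, or worsening), CLIF-C ACLF score, Child-Pugh score" and continues with the MELD score. It has no time point and no transplantation or death clause in the SAP or the protocol.

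**ACLF course, analysis.** SAP 9.3.7 says "ACLF Course will be summarized by visit, and at the end of hospitalization i.e. hospital discharge visit" and "The ACLF course at the hospital discharge visit will be compared between treatment groups".

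**Protocol test.** Protocol 9.1.2.4 sets the Fisher or Chi-square comparison of both outcomes at the end of hospitalization, without defining that as the discharge visit. The SAP adds that equation. Section 12 of the SAP, which lists changes in planned analysis, does not mention it.

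**The concern.** A discharge visit exists only for patients who leave hospital. If the treatment changes who survives, the tested patients in the two arms are no longer comparable as randomized. Extra survivors in the PE-A 5% arm are likely to be sicker than those who would have been discharged anyway, and they enter only that arm's denominator. A real benefit could then appear as no difference or as harm in two tables that describe how the disease evolved.

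For organ failure there is also a plain conflict between the SAP's endpoint definition and its analysis section.

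**Working it through.** **1. Who has no value at the discharge visit**

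- In-hospital deaths: SAP 9.3.1.1 describes these as occurring before the discharge visit.
- Patients transplanted before discharge: 9.3.7 and 9.3.8 both remove post-transplant assessments, which takes out their discharge assessment.
- Patients not discharged before the end of study: they have no discharge visit.

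SAP 6.1.1 leaves a missing visit missing. Neither 9.3.7 nor 9.3.8 gives a last-value rule, a death category or a composite. The adjusted analyses of these two outcomes in 9.3.11 use the same end-of-hospitalization outcome and inherit the gap. On observed data, the comparison is between patients discharged alive and untransplanted.

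**2. Denominator**

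SAP 9.3.9 states an ITT denominator for new infections; 9.3.7 and 9.3.8 state none. If all ITT subjects were the denominator for organ failure, a patient who died would count as having no organ failure.

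**3. Illustrative size**

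Inputs from the documents: 190 per arm; 90-day mortality 50% vs 35%; 28-day mortality 34% for ACLF-1b/2/3a at diagnosis (Protocol Table 2-2). The design hazard ratio reproduces: ln(0.65)/ln(0.50) = 0.6215.

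Assumptions, because the documents give no in-hospital death or transplant rate: a control share q has no usable value, and the PE-A 5% share is 1 − (1 − q)^0.6215. At q = 34% this is 1 − 0.66^0.6215 = 22.8%.

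| q (control) | PE-A 5% share | Leave the test, SMT vs PE-A 5% | Tested, SMT vs PE-A 5% |
|---|---|---|---|
| 20% | 12.9% | 38 vs 25 | 152 vs 165 |
| 34% | 22.8% | 65 vs 43 | 125 vs 147 |
| 50% | 35.0% | 95 vs 66 | 95 vs 124 |

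**4. Direction of the distortion**

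Suppose patients who would be discharged under either arm resolve at rate r in both arms, and the extra survivors resolve at rate s. At q = 34% there are 147 − 125 = 22 extra survivors.

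- At discharge: r for SMT, (125r + 22s)/147 for PE-A 5%. The second is lower whenever s < r.
- Over all randomized: 125r/190 vs (125r + 22s)/190. The second is higher whenever s > 0.

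So the sign reverses for any s strictly between 0 and r. With r = 70% (assumed):

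- s = 40%: discharge 87.5/125 = 70.0% vs (87.5 + 8.8)/147 = 65.5%; all randomized 46.1% vs 50.7%.
- s = 60%: discharge 70.0% vs (87.5 + 13.2)/147 = 68.5%; all randomized 46.1% vs 53.0%.
- s = 70%: no gap at discharge. Above 70%, the discharge comparison favours PE-A 5%.

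For organ failure, assume 20% at discharge in patients discharged under either arm and 60% (range 40–80%) in the extra survivors, again at q = 34%:

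- Discharge visit: 20.0% vs 25.8% (22.9–28.7%).
- Death or organ failure: 47.2% vs 42.7% (40.5–45.0%).
- ITT denominator with deaths counted as no failure: 13.2% vs 19.9%. The gap is 6.7 points, against 5.8 at the discharge visit.

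**The case against.** **The ACLF-course endpoint has lost nothing.** A reader might infer that the transplantation or death wording was dropped from both endpoints. It belongs only to the organ-failure line. For ACLF course the restriction is real, but no endpoint wording is contradicted. This stands.

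**The protocol does not prescribe a last value before death for these tests.** A reader might take the phrase about values before transplantation or death in Protocol 9.1.2.4 that way. There it governs the change-from-baseline ANCOVA. The Fisher or Chi-square sentence names only the end of hospitalization. This also stands.

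**Data from patients who die are used elsewhere.** Organ sub-scores are compared across common visits in SAP 9.3.2, and time to in-hospital death, with or without transplantation, is analysed in 9.3.1.1 and 9.3.1.2. True, but these are separate analyses and do not correct the comparisons in 9.3.7, 9.3.8 and 9.3.11.

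**The numbers are chosen.** The 70% and 40% resolution rates and the 20% and 60% organ-failure rates are in neither document. A 90-day hazard ratio is applied to 28-day mortality, which stands in for in-hospital death, and transplants are ignored. The study stopped early, so 190 per arm is the design size. Even at 70.0% of 125 vs 65.5% of 147, an uncorrected Chi-square gives p of about 0.43. All of this limits the figures to showing direction; it does not remove the selection by survival.

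**Conclusion.** The concern holds in a limited form. For organ failure, SAP 9.3.8 is narrower than the endpoint in SAP 4.1.3 and 5.4.1 and Protocol 7.1.3, and Section 12 does not say so. For ACLF course, SAP 9.3.7 imposes the same restriction on an endpoint with no stated time point. Read with 6.1.1 and the removal of post-transplant data, both tests and their adjusted versions compare a set selected by the primary outcome, with no denominator stated.

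Under the stated assumptions roughly 65 vs 43 of 190 per arm drop out, with a range of 38 vs 25 to 95 vs 66. The reversal of direction requires the extra survivors to do worse than other discharged patients; that is plausible but not documented. The documents do not support a prediction that these tests will show harm.

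The endpoints are exploratory and outside the fixed sequence. The by-visit models and the primary and secondary conclusions are not affected. The change is worth making but is not critical.

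**What to change.** In SAP 9.3.7 and 9.3.8:

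1. Define end of hospitalization as the earliest of discharge, liver transplantation, in-hospital death or last study visit.
2. For patients discharged, transplanted or still in hospital, use the last assessment on or before that date, taken before the transplant for transplanted patients.
3. In the ACLF course table, count an in-hospital death once only, as its own worst category, whatever the last recorded grade.
4. For each organ, report the last value before death, as the endpoint defines it, alongside a composite of death or failure of that organ.
5. State the ITT denominator, use the same outcomes in 9.3.11, and declare the definition in Section 12.

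The data should already exist. Protocol Appendix 1 schedules ACLF grade and severity scores daily from Day 1 to Day 17, Protocol 7.2.1.2 continues treatment-period assessments in inpatients until discharge, and SAP 9.3.2 already lists the CLIF-C OF scores before transplantation or death. The cost is a small derivation and one extra row or composite per table.
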